Study Protocol P3-C1-001

Characterising the use of JAK inhibitors in Europe: a Drug Utilisation Study

29/01/2025

Version 3.0

Author(s): [name], [name]

Version: V3.0

Dissemination level: Public

Contents

LIST	OF	ABBREVIATIONS	4
1.	TI	TLE	5
2.	RE	SPONSIBLE PARTIES – STUDY TEAM	5
3.	ΑE	3STRACT	6
4.	Αſ	MENDMENTS AND UPDATES	8
5.		ILESTONES	
		ATIONALE AND BACKGROUND	_
6.			
7.	RE	SEARCH QUESTION AND OBJECTIVES	9
8.	RE	SEARCH METHODS	10
8	.1	Study type and study design	
_	.2	Study setting and data sources	
_	.3	Study period	
	.4	Follow-up	
	.5	Study population with inclusion and exclusion criteria	
_	.6	Variables	
	.7	Study size	
_	.8	Analysis	
	.9	Evidence synthesis	
9.	DA	ATA MANAGEMENT	
10.		QUALITY CONTROL	25
11.		LIMITATIONS OF THE RESEARCH METHODS	26
12.		MANAGEMENT AND REPORTING OF ADVERSE EVENTS/ADVERSE REACTIONS	26
13.		GOVERNANCE BOARD ASPECTS	26
14.		PLANS FOR DISSEMINATING AND COMMUNICATING STUDY RESULTS	26
15.		OTHER ASPECTS	
16.		REFERENCES	
17.		ANNEXES	28

P3-C1-001 Study Protocol

Version: V3.0

Study title	DARWIN EU® - Characterising the use of JAK inhibitors in Europe: a Drug Utilisation Study	
Protocol version	V3.0	
Date	29/01/2025	
EU PAS number	EUPAS1000000424	
Active substance	JAKi (abrocitinib, baricitinib, filgotinib, tofacitinib, upadacitinib)	
Medicinal product	N/A	
Research question and objectives	 This study aims to identify and characterise new JAKi users. The specific objectives are: To estimate the incidence of new JAKi use, overall and for each individual JAKi ingredient. To characterise new JAKi users and treatment for each individual JAKi, stratified by indication 	
Country(ies) of study	Finland, Germany, Netherlands, Norway, and Spain	
Author(s)	[name], [name]	

P3-C1-001	Study	Protocol
-----------	-------	----------

Version: V3.0

Dissemination level: Public

LIST OF ABBREVIATIONS

Acronyms/terms	Description	
CDM	Common Data Model	
DA	Disease Analyzer	
DARWIN EU®	Data Analysis and Real World Interrogation Network	
DUS	Drug Utilisation Study	
EEA	European Economic Area	
EHR	Electronic Health Records	
EMA	European Medicines Agency	
EU	European Union	
FDA	Food and Drug Administration	
FinOMOP-HILMO	Finnish Care Register for Health Care	
GP	General Practitioner	
IPCI	Integrated Primary Care Information	
JAKi	Janus kinase inhibitor/s	
MACE	Major adverse cardiovascular event	
NLHR	Norwegian Linked Health Registry data	
OHDSI	Observational Health Data Sciences and Informatics	
ОМОР	Observational Medical Outcomes Partnership	
ORAL	Oral Rheumatoid Arthritics Trial	
TNF	Tumour Necrosis Factor	
VID	Valencia Health System Integrated Dataset	

1. TITLE

DARWIN EU® - Characterising the use of JAK inhibitors in Europe: a Drug Utilisation Study

3. ABSTRACT

Title

Characterising the use of JAK inhibitors in Europe: a Drug Utilisation Study

Rationale and background

JAKi therapy has been gaining popularity for the treatment of several autoimmune conditions, including rheumatoid arthritis, inflammatory bowel disease, and atopic dermatitis. The first JAKi, tofacitinib, was approved by the European Medicines Agency (EMA) for the management of rheumatoid arthritis in 2017. An FDA-requested study (the Oral Rheumatoid Arthritics Trial (ORAL) Surveillance trial) showed a higher risk of major adverse cardiovascular events (MACE), cancer and adjudicated opportunistic infection with tofacitinib compared to tumour necrosis factor (TNF) inhibitors in patients aged 50 years or older with at least one cardiovascular risk factor. Further research has been conducted on the safety profile of JAKi for other indications, including psoriatic arthritis, ulcerative colitis and atopic dermatitis. It was shown that risk of venous thrombotic events of JAKi users was similar to placebo users in patients with atopic dermatitis and ulcerative colitis. Incidence of adverse events, including herpes zoster infection and thrombotic events, remained similar with longer follow-up up to two years in psoriatic arthritis patients with JAKi. However, especially in these newer indications, the available evidence has been limited by short duration of follow-up and limited sample size.

The current study aims to identify the incidence of new JAKi use over time, and to characterise new users of JAKi in Europe to inform the feasibility of future safety studies.

Research question and objectives

This study aims to characterise the use of JAKi in Europe.

The specific objectives are:

- 1. To estimate the incidence of new JAKi use, overall and for each individual JAKi ingredient.
- 2. To characterise new JAKi users and treatment for each individual JAKi ingredient, over all indications and stratified by indication.

Methods

Study design

- Population level cohort study (objective 1)
- New user cohort study (objectives 2)

Population

The population level cohort study will include all subjects available in the selected databases from 1st January 2017 until the most recent data lock of their respective databases, with at least 365 days of data visibility.

The patient level cohort study will include all JAKi new users from the 1st January 2017 until the most recent data lock of their respective databases, with at least 365 days of data visibility.

Variables

Drugs of interest: JAKi: abrocitinib, filgotinib, baricitinib, upadacitinib, tofacitinib

P3-0	1-00	11 Sti	ıdv Pr	otocol

Version: V3.0

Dissemination level: Public

Indications: atopic dermatitis, juvenile idiopathic arthritis, inflammatory bowel disease, alopecia areata, axial spondyloarthritis, psoriatic arthritis, rheumatoid arthritis, unknown indication

Patient characteristics: age, sex, time from first diagnosis of indication to JAKi therapy initiation

Treatment characteristics: duration of index treatment drug era

Stratification: ingredient (specific JAKi), and indication

Data source

- 1. FinOMOP-HILMO (Finland)
- 2. IPCI (The Netherlands)
- 3. IQVIA DA Germany (Germany)
- 4. NLHR (Norway)
- 5. VID (Spain)

Sample size

No sample size has been calculated for this study. Based on the preliminary feasibility assessment, expected number of subjects to be involved in each data source would be approximately between 600 and 7900.

Statistical analysis

Incidence of new JAKi use, overall and for each individual JAKi ingredient, will be calculated yearly as the number of new users per 100,000 person-years of the population at risk of getting exposed during the period for each calendar year, with 95% Poisson exact confidence intervals. Patient characterisation on new JAKi users will be done based on age, sex and indication for each JAKi ingredient, over all indications and stratified by indication. Patient characterisation on time from first diagnosis of indication to first JAKi initiation, and treatment duration of the first drug era will be reported for each JAKi ingredient stratified by indication. Time from first diagnosis of indication to treatment initiation and treatment duration will be summarised, providing the minimum, p25, median, p75, and maximum duration.

4. AMENDMENTS AND UPDATES

None.

5. MILESTONES

Study milestones and deliverables	Planned dates
Draft Study Protocol	29/11/2024
Final Study Protocol	December 2024
Creation of Analytical code	January-February 2025
Execution of Analytical Code on the data	January-February 2025
Draft Study Report	March 2025
Final Study Report	April 2025

6. RATIONALE AND BACKGROUND

JAKi therapy has been gaining popularity for the treatment of several autoimmune conditions, including rheumatoid arthritis, inflammatory bowel disease, and atopic dermatitis. The first JAKi, tofacitinib, was approved by the European Medicines Agency (EMA) for the management of rheumatoid arthritis in 2017.1 An FDA-requested study (the Oral Rheumatoid Arthritics Trial (ORAL) Surveillance trial)² showed a higher risk of major adverse cardiovascular events (MACE), cancer and adjudicated opportunistic infection with tofacitinib compared to tumour necrosis factor (TNF) inhibitors in patients aged 50 years or older with at least one cardiovascular risk factor.³ Further research has been conducted on the safety profile of JAKi for other indications, including psoriatic arthritis, ulcerative colitis and atopic dermatitis.⁴⁻⁶ It was shown that risk of venous thrombotic events of JAK inhibitor users was similar to placebo users in patients with atopic dermatitis⁶ and ulcerative colitis⁵. Incidence of adverse events, including herpes zoster infection and thrombotic events, remained similar with longer follow-up up to two years in psoriatic arthritis patients with JAK inhibitor.⁴ A recent meta-analysis focusing on the JAKi use for immune-mediated skin conditions, including atopic dermatitis, alopecia areata and vitiligo, also showed no significant difference between JAKi and placebo or active comparators in the composite outcome of MACE and all-cause mortality, as well as risk of venous thrombotic events. However, the available evidence, especially in other indications than RA, has been limited by short duration of follow-up and limited sample size and more research is needed to understand the safety profile in these populations. Since the new indications are relatively recently approved and the use of JAKi within those has not been that common, the sample size for these indications is an issue and hampers future research, therefore a study in a federated network such as DARWIN EU might be a solution.

The current study aims to identify the incidence of new JAKi use over time, and to characterise new users of JAKi in Europe to inform the feasibility of future safety studies.

P3-C1-001 Study Protocol	
Author(s): [name], [name]	Version: V3.0
	Dissemination level: Public

7. RESEARCH QUESTION AND OBJECTIVES

Table 1. Primary and secondary research questions and objective.

A. Objective 1. Population-level drug utilisation

Objective 1:	To estimate the incidence of new JAKi use, overall and for each individual JAKi ingredient	
Hypothesis:	Not applicable	
Population (mention key inclusion- exclusion criteria):	The study includes all people available in the databases with at least 365 days of data visibility.	
Exposure:	Not applicable	
Comparator:	Not applicable	
Outcome:	JAKi (abrocitinib, filgotinib, baricitinib, upadacitinib, tofacitinib)	
Time (when follow up begins and ends):	From 1 st January 2017 until the most recent data lock for each included database.	
Setting:	Data will be collected from primary care and secondary care outpatient setting with the following databases:	
	- FinOMOP-HILMO (primary care, secondary care outpatient)	
	- IPCI (primary care)	
	- IQVIA DA Germany (primary care)	
	- NLHR (primary care, secondary care outpatient)	
	- VID (primary care, secondary care outpatient)	
Main measure of effect:	Annual incidence rates of JAKi use, for the entire class pooled together and for each JAKi ingredient	

B. Objectives 2. Patient-level characterisation and drug utilisation studies

Objective 2:	To characterise new JAKi users and treatment, overall and stratified by ingredient and indication	
Hypothesis:	Not applicable	
Population (mention key inclusion- exclusion criteria):	The study includes all patients available in the databases initiating JAKi therapy, with at least 365 days of data visibility before therapy initiation	
Exposure:	JAKi (abrocitinib, filgotinib, baricitinib, upadacitinib, tofacitinib)	
Comparator:	Not available	
Outcome:	Not available	
Time (when follow up begins and ends):	For treatment characterisation: from each JAKi therapy initiation until the discontinuation of index drug	
Setting:	Data will be collected from primary care and secondary care outpatient setting with the following databases: - FinOMOP-HILMO (primary care, secondary care outpatient)	

DARWIN M	P3-C1-001 Study Protocol	
○EU/V	Author(s): [name], [name]	Version: V3.0
,		Dissemination level: Public

	 IPCI (primary care) IQVIA DA Germany (primary care) NLHR (primary care, secondary care outpatient) VID (primary care, secondary care outpatient)
Main measures of effect:	Patient characterisation: demographics and time from first diagnosis of indication to each JAKi therapy initiation Treatment characterisation: treatment duration in months

8. RESEARCH METHODS

8.1 Study type and study design

Cohort studies will be conducted using the data from the included databases. A population-level cohort analysis will be used for Objective 1. A new drug users cohort design will be used for Objectives 2 and 3.

Table 2. Description of potential study types and related study designs.

Study type	Study design	Study classification	
Population Level DUS	Population Level Cohort	Off the shelf	
Patient Level DUS	New drug/s user cohort	Off the shelf	

8.2 Study setting and data sources

This study will be conducted using 5 databases onboarded for DARWIN EU® network of data partners from 5 European countries. These databases have been selected based on geographic representativeness and availability of data on JAK inhibitors. The selected databases cover Finland, Germany, Norway, The Netherlands and Spain. The results generated from these databases will therefore cover regions of Northern, Central and Southern Europe.

Detailed information of the selected data sources is described in Table 3.

Author(s): [name], [name]

Version: V3.0

Dissemination level: Public

Table 3. Description of the selected data sources.

Country	Name of Database	Justification for Inclusion	Health Care setting	Type of Data)	Number of active subjects	Feasibility count of exposure ¹	Data lock for the last update
Finland	FinOMOP-	Databases include adequate	Drimany care CD primary	EHR,	6.25M	2500	2024-04-16
rinianu	HILMO	Databases include adequate number of records of JAK inhibitors for subsequent patient characterisation.	Primary care GP, primary care specialist, secondary care specialist, hospital inpatient care	registries	6.23IVI	2500	2024-04-16
The Netherlands	IPCI	Databases include adequate number of records of JAK inhibitors for subsequent patient characterisation.	Primary care GP	EHR	1.25M	700	2024-04-30
Germany	IQVIA DA Germany	Databases include adequate number of records of JAK inhibitors for subsequent patient characterisation.	Primary care GP, primary care specialist	EHR	4.35M	7900	2023-09-30
Norway	NLHR	Databases include adequate number of records of JAK inhibitors for subsequent patient characterisation.	Primary care GP, primary care specialist, secondary care specialist, hospital inpatient care	Registries	5.74M	2600	2024-06-30
Spain	VID ²	Databases include adequate number of records of JAK inhibitors for subsequent patient characterisation.	Primary care GP, secondary care specialist, hospital inpatient care, nursing homes	EHR, registries	1.61M	600	2022-01-01

^{1.} Feasibility count of exposure was identified as unique exposed individuals.

^{2.} Only female individuals are included in this data source.

P3-0	1-00	11 Sti	ıdv Pr	otocol

Version: V3.0

Dissemination level: Public

Information on data sources used is described below:

Finnish Care Register for Health Care [FinOMOP-HILMO] (Finland)

The THL HILMO database covers both public and private, primary and specialised inpatient and outpatient health care encounters in Finland starting from 2011. The entire public sector and private inpatient encounters have been included since 2011, while private outpatient encounters, including occupational care, are included since 2020. The main content of the THL CDM is The Finnish Care Register for Health Care (fi:Hoitoilmoitusrekisteri, HILMO). It is a continuation of the former Hospital Discharge Register, which originally gathered data on patients discharged from hospitals. The Care Register has comprehensive data on the use of services and service users from Finnish public inpatient and outpatient primary and specialised care nationwide. Since 1998 the register has covered both public outpatient and inpatient specialised care and private inpatient care (TerveysHilmo). From 2011 the register has covered public primary care (AvoHilmo). From 2020 the register has covered private outpatient care and occupational care. In addition, the CDM also contains the vaccination data from the Finnish National Vaccination Register, and positive COVID-19 test results from the Finnish National Infectious Diseases Register, which is maintained by THL. The CDM is currently produced from the above-mentioned, and limited to observation periods commencing after 1.1.2011. The National Population registry is also used as a source for the CDM database. The National Population registry data forms the basis for forming the patient population. This ensures up-to-date location (municipality of residence) of patients as well as complete death occurrences (although not the cause of death). Using the complete population as a basis for the person table also serves to facilitate calculations on a population level, e.g. incidence rates. The current CDM population comprises all persons having been alive and residing in Finland since the beginning of 2011.

Integrated Primary Care Information [IPCI] (The Netherlands)

The Integrated Primary Care Information (IPCI) database is a longitudinal observational database containing routinely collected data from computer-based patient records of a selected group of GPs throughout the Netherlands (N=723). IPCI was started in 1992 by the department of Medical Informatics of the Erasmus University Medical Center in Rotterdam with the objective to enable better post marketing surveillance of drugs. The current database includes patient records from 2006 on, when the size of the database started to increase significantly. In 2016, IPCI was certified as Regional Data Center. Since 2019 the data is also standardised to the Observational Medical Outcomes Partnership common data model (OMOP CDM), enabling collaborative research in a large network of databases within the Observational Health Data Sciences and Informatics (OHDSI) community. The primary goal of IPCI is to enable medical research. In addition, reports are generated to inform GPs and their organisations about the provided care. Contributing GPs are encouraged to use this information for their internal quality evaluation. The IPCI database is registered on the European Medicines Agency (EMA) ENCePP resources database (http://www.encepp.eu).

IQVIA Disease Analyzer Germany [IQVIA DA Germany] (Germany)

IQVIA Disease Analyzer (DA) Germany is a database of de-identified electronic medical records from specialised and general primary practices (GP) in Germany since 1992. This dataset encompasses approximately 3% of all outpatient practices within Germany, ensuring a substantial representation of the national healthcare landscape. The sampling methods used for practice selection, taking into account physician's demographics, specialty focus, community size category and federal state location, was instrumental in constructing a database that accurately mirrors the diverse spectrum of healthcare providers in the country. Consequently, data within IQVIA DA Germany database has been demonstrated to be representative of general and specialised practices throughout Germany.

P3-C1-001 Study	v Protocol
-----------------	------------

Version: V3.0

Dissemination level: Public

The database contains demographics records, basic medical data, disease diagnosis according to International Classification of Diseases, 10th revision (ICD-10), and prescription records. While the database partly records information on deaths and procedures, it currently does not support linkage with external data sources. Routine updates are conducted at regular intervals.

IQVIA DA Germany is suitable for pharmacoepidemiologic and pharmacoeconomic studies as previously demonstrated. The quality of data is assessed based on several criteria including completeness of information and correctness (e.g. linkage between diagnosis and prescriptions).

Norwegian Linked Health Registry data [NLHR] (Norway)

Norway has a universal public health care system consisting of primary and specialist health care services covering a population of approximately 5.4 million inhabitants. Many population-based health registries were established in the 1960s with use of unique personal identifiers facilitating linkage between registries. Data in these health registries are used for health analysis, health statistics, improving the quality of healthcare, research, administration and emergency preparedness. We harmonised data from the following registries: the Medical Birth Registry of Norway (MBRN), the Norwegian Prescription Registry (NorPD), the Norwegian Patient Registry (NPR), Norway Control and Payment of Health Reimbursement (KUHR), the Norwegian Surveillance System for Communicable Diseases (MSIS), the Norwegian Immunisation Registry (SYSVAK), the National Death Registry, and the National Registry (NR). Linkage between the registries was facilitated using project-specific person ID generated from unique personal identification assigned at birth or immigration for all legal residents in Norway. In brief: MBRN stores information about the pregnancy, the mother, father and child; NPR records diagnosis in secondary care (e.g., hospital); KUHR contains information about diagnosis and contact in primary care (e.g., GPs and outpatient specialists) – to be included in third release; NorPD recorded all medications dispensed outside of hospitals; MSIS collects test results of communicable diseases (e.g., Sars-Cov-2); SYSVAK recorded vaccinations.

Valencia Health System Integrated Dataset [VID] (Spain)

The Valencia Health System Integrated Dataset (VID) is a set of multiple, public, population-wide electronic databases for the Valencia Region, the fourth most populated Spanish region, with about 5 million inhabitants and an annual birth cohort of 48 000 newborns, representing 10.7% of the Spanish population and around 1% of the European population. The VID provides exhaustive longitudinal information including sociodemographic and administrative data (sex, age, nationality, etc.), clinical (diagnoses, procedures, diagnostic tests, imaging, etc.), pharmaceutical (prescription, dispensing) and healthcare utilisation data from hospital care, emergency departments, specialised care (including mental and obstetrics care), primary care and other public health services. It also includes a set of associated population databases and registries of significant care areas such as cancer, rare diseases, vaccines, congenital anomalies, microbiology (including COVID-19 test results registry) and others, and also public health databases from the population screening programmes. All the information in the VID databases can be linked at the individual level through a single personal identification code. The databases were initiated at different moments in time, but all in all the VID provides comprehensive individual-level data fed by all the databases from 2008 to date. The OMOP instance has been created using CONSIGN project data, where 1.96 million of females in fertile age are studied from start of 2018 to end of 2021.

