8.3 Study period

The study period starts from 1st January 2017 until the most recent data lock for each included database (see **Table 3**).

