8.6 Variables

8.6.1 Exposure/s

In the population level DUS (Objective 1) no exposure variable will be defined. The incident use of JAKi will be the outcome in the analyses, as described in section 8.6.2 below.

Exposure of interest in the characterization of JAKi initiators (Objective 2) will be the initiation of treatment with the following JAKi, including abrocitinib, filgotinib, baricitinib, upadacitinib, and tofacitinib. Operational definition of exposure is described in **Table 4**.

Author(s): [name], [name]

Version: V3.0

Dissemination level: Public

Table 4. Operational definitions of exposure.

Exposure group name(s)	Details	Washout window	Assessment Window	Care Setting ¹	Code Type	Applied to study populations	Incident with respect to	Measurement characteristics / validation	Source of algorithm
Individual JAKi ingredient	Preliminary code lists provided in Appendix I.	[-Inf, -1]	First ever exposure of each individual JAKi ingredient will be assessed during the study period of 2017-2024.	ОР	RxNorm	For patient level characterization (objective 2)	Specific individual JAKi ingredient	N/A	N/A

¹ IP = inpatient, OP = outpatient, ED = emergency department, OT = other, n/a = not applicable

P3-C1-001 Stud	dy Protocol
----------------	-------------

Version: V3.0

Dissemination level: Public

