8.8.2 Methods to derive parameters of interest

Incidence of new JAKi use

Incidence of new JAKi use (measured as prescription or dispensation), overall and for each individual JAKi ingredient, will be calculated annually as the number of individuals with a first JAKi prescription/dispensation per 100,000 per-years of the population at risk of getting exposed during the period for each calendar year. Those study participants who enter the denominator population will then contribute time at risk up to their first use during the study period or if they do not have a drug exposure, they will contribute time at risk up as described above in section 8.4 (Follow-up). Incidence rates will be given together with 95% Poisson exact confidence intervals. Illustration of the calculation of incidence use of the medicines of interest is shown below in Figure 3.

[figure not shown]

Figure 3. Illustration of the calculation of incidence on use of medicines of interest.

Example of incidence calculation is shown in **Figure 3**. Individuals (ID 1, 2) with sufficient data visibility will be included in the incidence calculation contributing to the time at risk (denominator). Individuals will be continued to contribute the time at risk until initiation of drug of interest (ID 1) or the end of follow-up for yearly cohort (ID 2). For individuals with exposure to JAKi before the start of the yearly cohort (ID 3) or with exposure at the start of the yearly cohort (ID 4), these subjects will not be included for the annual incidence calculation. Individuals will contribute time at risk only when they have with sufficient data visibility. Therefore, as illustrated by ID 5 and 6, individuals are only included and contribute to the denominator from the point with at least 365 days of data visibility.

For the incidence of each individual JAKi ingredient, only use of the specific individual JAKi ingredient will be considered. These subjects with previous exposure of other JAKi will be allowed to be included in the denominator during the calculation of population-level incidence. Each analysis on individual JAKi ingredient will be independent of other JAKi exposure. In another words, patients with exposure to different JAKi will be counted multiple times in different analyses.

Patient Characteristics

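### FinOMOP-HILMO sees private outpatient care only from 2020, yet the Finnish incidence series and the first-ever washout run unbroken from 2017, so 2020 is at risk of an artificial step and of established users counted as new

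*Protocol*

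**What the plan says.** The HILMO description in section 8.2 gives the change in coverage twice: "private outpatient encounters, including occupational care, are included since 2020", and again "From 2020 the register has covered private outpatient care and occupational care". Public care and private inpatient care are covered since 2011. The opening sentence of the same description, read alone, suggests that private outpatient care is also covered since 2011.

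The rest of the plan does not use the 2020 date:

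- Section 8.3: "The study period starts from 1st January 2017 until the most recent data lock for each included database".
- Section 7, Table 1 lists the Finnish setting as "FinOMOP-HILMO (primary care, secondary care outpatient"; Table 4 in section 8.6.1 gives the care setting as outpatient.
- Table 4 sets the washout at [-Inf, -1]: "First ever exposure of each individual JAKi ingredient will be assessed during the study period of 2017-2024".
- Section 8.8.2: incidence "will be calculated annually as the number of individuals with a first JAKi prescription/dispensation".
- On the Finnish denominator, section 8.2 says "The National Population registry data forms the basis for forming the patient population" and "The current CDM population comprises all persons having been alive and residing in Finland since the beginning of 2011".

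Section 11 discusses a database-specific denominator artefact for IQVIA DA Germany only. It says nothing about Finland.

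**The concern.** One sector of outpatient care becomes visible inside the study period, while the denominator includes all residents throughout. People treated only in private outpatient care in 2017-2019 contribute person-time, but their JAKi starts cannot be seen. The 365-day visibility rule in section 8.4 does not help, because it counts observation time and not whether a sector is covered. The unlimited look-back does not help either: it finds earlier use only where that use was recorded. A patient started privately in 2018 and still treated in 2020 would pass the washout and enter as new.

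For Objective 1, section 6 states the aim as incidence over time and section 14 plots annual rates. A Finnish rise from 2019 to 2020 could therefore mix uptake with the change in capture. For Objective 2, a misclassified entrant would have a late index date and a shortened first treatment era. The effect on time from diagnosis could go either way. If the diagnosis was made in covered care, the interval is too long. If it was made in private outpatient care before 2020, it is equally unseen, so the interval may be too short or the patient may fall into the unknown-indication group.

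**Working it through.** The protocol gives no figure on this point, so there is none to reproduce. The check is a scenario calculation.

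**Inputs from the protocol.** Coverage change in 2020 (section 8.2); study start 1 January 2017 (section 8.3); 2,500 exposed individuals, 6.25 million active subjects and data lock 16 April 2024 for FinOMOP-HILMO (Table 3).

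**Assumptions, not in the protocol.**
- p is the share of JAKi starts recorded only in private outpatient care.
- k is the share of the 2017-2019 private-only starters who are still treated in 2020 and so first seen then, taken as 0.3 to 0.6. It excludes anyone with a JAKi record in public care before 2020, because the washout already removes them.
- Private care is captured for the whole of 2020.

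**Flat true incidence.** Take one unit of true starts per year. Observed 2019 = 1 - p. Observed 2020 = 1 + 3pk, where the second term is the backlog from three unseen years. Hence:

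- apparent 2020/2019 ratio = (1 + 3pk)/(1 - p)
- established users among 2020 entrants = 3pk/(1 + 3pk)
- lasting level shift from 2021 = 1/(1 - p)

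**Rising uptake.** With true starts of 1, 2, 3 and 4 units in 2017-2020, observed 2019 = 3(1 - p) and observed 2020 = 4 + 6pk. The true ratio is 4/3 = 1.33, so it is inflated by (1 + 1.5pk)/(1 - p).

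| p | Ratio, flat (k = 0.3 to 0.6) | Established among 2020 entrants, flat | Inflation, rising uptake | Level shift, flat |
|---|---|---|---|---|
| 0% | 1.00 | 0% | 1.00 | 1.00 |
| 1% | 1.009/0.99 = 1.02 to 1.018/0.99 = 1.03 | 0.9% to 1.8% | 1.01 to 1.02 | 1.01 |
| 5% | 1.045/0.95 = 1.10 to 1.09/0.95 = 1.15 | 4.3% to 8.3% | 1.0225/0.95 = 1.08 to 1.045/0.95 = 1.10 | 1.05 |
| 10% | 1.09/0.90 = 1.21 to 1.18/0.90 = 1.31 | 8.3% to 15.3% | 1.045/0.90 = 1.16 to 1.09/0.90 = 1.21 | 1.11 |
| 20% | 1.18/0.80 = 1.48 to 1.36/0.80 = 1.70 | 15.3% to 26.5% | 1.09/0.80 = 1.36 to 1.18/0.80 = 1.48 | 1.25 |

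**Against sampling error.** Treat the feasibility count as new users spread evenly over 1 January 2017 to 16 April 2024 (7.29 years). Then 2,500/7.29 = 343 per year, and 343/6.25 million = 5.5 per 100,000 person-years (exact 95% interval for one year 4.9 to 6.1). A ratio of two such years has a 95% margin of about exp(1.96 × √(2/343)) = 1.16 in either direction. Under the rising pattern the same total gives about 247 starts in 2019 and 330 in 2020, with a margin of exp(1.96 × √(1/247 + 1/330)) = 1.18. The artefact is lost in noise at p = 1%. At 5% it is still within the margin. At 10% it exceeds the margin under flat incidence and lies around it under rising uptake. At 20% it exceeds it in both.

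**The case against.** The strongest objection is that the step depends on a fact that the protocol does not give. Section 8.2 describes encounter coverage and names no source for Finnish drug records. If JAKi records come mainly from public specialist care, which is visible throughout, p is near zero and nothing happens. The study is also descriptive, with no hypothesis, trend test or pooling, so any distortion stays within the Finnish results.

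Much of this stands. It rules out three stronger readings that a reader might infer:

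- *That 2020 will show a jump.* The documents support a risk, not a certainty.
- *That misclassified users will have too long a time from diagnosis.* Private outpatient diagnoses before 2020 are unseen too, so the direction is open.
- *That 2020 should be dropped from the main Finnish series.* At the flat rate this would remove about 343 of 2,500 users (14%), including genuine starters in public care, for an effect of unknown size.

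The objection does not remove the point. The listed Finnish sources are the care register, vaccination data, COVID-19 test results and the population registry. Only the care register could plausibly carry JAKi records, whereas the Norwegian description names a prescription registry. On the text as it stands, the natural reading is that capture follows encounter coverage. If another source exists, the protocol should name it. Section 11 also shows that database-specific artefacts are considered worth stating.

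**Conclusion.** The point holds as a risk of unknown size. The Finnish series crosses a change in coverage in 2020 that neither the methods nor the limitations address, while the denominator stays at all residents. If JAKi records follow encounter coverage, and prescribing behaviour does not itself change, the bias can only raise 2020 relative to 2017-2019. It has two parts: a one-off backlog of established users and a lasting level shift. The size ranges from negligible (2% to 3% at a private-only share of 1%) to material (21% to 31% at 10% with flat incidence, 16% to 21% with the rising pattern). The share, the retention and the uptake shapes are all assumptions. The remedy is cheap, so it is worth making before the results are plotted.

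**What to change.** 1. State in section 8.2 where Finnish JAKi records come from and whether private outpatient prescriptions are visible before 2020. Reconcile the opening sentence of the HILMO description with the 2020 date, and give the exact date on which private capture starts.
2. Keep the main Finnish series, mark a break at 2020 in table and plot, and state that no trend is read across it.
3. Add one HILMO sensitivity analysis. If the source of each record is coded, run a constant-capture series without private outpatient records for the whole period. If not, run a full-capture series that starts after one year of private-care visibility.
4. Repeat the Finnish Objective 2 tables without 2020 entrants, as a sensitivity analysis only. This does not restore private diagnoses from before 2020 for later starters, so the caveat must mention them.
5. Add the caveat to section 11 beside the German one.

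The cost is protocol wording, one extra HILMO run and a Finnish trend shown in two pieces. If step 1 shows that drug records do not depend on encounter coverage, the incidence analysis in step 3 can be dropped with a sentence saying so.
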